Table 6 outlines projected recruitment targets for both groups. Advanced testing will be offered to all participants to the cap in table 6, on the basis of fully informed consent. Progress in recruitment to both groups will be monitored by the project manager and monitor.

	F/F		F/M		F/G		TOTALS		S
	6-		6-		6-		6-		
Ages	11	12+	11	12+	11	12+	11	12+	All
ADVANCED	47	60	17	26	17	0	64	86	150
STANDARD	27	36	9	15	0	0	36	51	87

Total 74 96 26 41 17 0 117 137 254	Total	74	96	26	41	17	0	117	137	254	
------------------------------------	-------	----	----	----	----	----	---	-----	-----	-----	--

Table 6. Projected recruitment to standard and advanced testing arms for parent study.

Primary and Secondary Outcomes

The primary outcome measure for this study is the absolute change from base line values and CT scores.

The secondary outcome measures are as follows;

- height/weight/BMI
- FEV1
- Airway microbial culture
- Airway microbiome determination
- Nasal Lavage inflammatory markers
- Nasal microbiome determination
- Exhaled Nitric Oxide
- Liver function testing
- Liver ultrasound Liver
- Examination score
- Sputum inflammatory markers
- Sputum microbiome determination
- Stool inflammatory markers
- Stool microbiome determination
- Sweat Chloride
- Genetic modifiers of CF phenotype
- Abdominal symptom score
- CFQ-R
- Treatment Adherence
- Medication Pick up rates

Core Data to be Collected

Eligibility assessment

Prior to study enrolment, the investigator will assess subject eligibility. This will include reviewing the subject's current medication and medical history in detail to ensure no exclusion criteria are met and all inclusion criteria are met. As part of the eligibility assessment, a urine pregnancy test (CE marked) must be conducted in female participants considered of childbearing potential (WOCBP). WOCBP are defined as females that are fertile, following menarche, until becoming post-menopausal unless permanently sterile. Permanent sterilisation methods include hysterectomy, bilateral salpingectomy and bilateral oophorectomy. A postmenopausal state is defined as no menses for 12 months without an alternative medical cause. A negative test must be produced prior to enrolment and documented within the subject's medical records.

Demographic data

Core demographic data will be collected on all individuals including genotype, sex, date of birth, CF centre and medications.

Sweat Chloride

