Sputum samples will be collected and stored on all participants annually, and these samples will be used for collaborative projects, however detailed analysis of these specimens will not be part of the extension study.

Sputum processing

As part of standard clinical care, sputum or oropharyngeal specimens (OPS) will be collected and processed in clinical laboratories. This data will be stored on local hospital systems and uploaded in the usual way from each center to the relevant national registry, our collaborators in this study. Separate to this, sputum samples for research purposes will be collected at study visits and immediately processed in the laboratory. Measurement of markers of inflammation in sputum is greatly facilitated by having a detailed and reproducible protocol for processing of fresh sputum specimens after collection. We will use such a system to ensure that our samples are collected, handled and processed to the highest level of quality during the study (138). Briefly, according to the TETRIS protocol, sputum will be collected from subjects, either spontaneously or after hypertonic saline induction, and immediately placed on ice for transport to the laboratory. The two-step temperature controlled process will be followed according to the protocol, however, once sputum plugs have been homogenized with cold phosphate buffered saline (PBS), and prior to centrifugation, an aliquot of this homogenized sputum will be mixed with an RNA preservative (RNAlater) and frozen at -80°C for later 16s shotgun sequencing. Sputum supernatant, once processed by TETRIS, will be aliquoted and stored at -80°C.

If a subject is not in a position to produce sputum, the research nurse/coordinator will arrange for sputum induction to be carried out. Sputum induction will be performed by using 7% hypertonic sodium chloride solution will be nebulized for 15 minutes with the subject encouraged to carry out airway clearance maneuvers during and after nebulization. All sputum collected over a 30-minute period will be utilized.

Nasal Lavage

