A breath sample will be collected from a cohort of 60 subjects in the 6-11 cohort at CHI at Crumlin, CHI at Temple Street, CHI at Tallaght and Guy's and St. Thomas' NHS Foundation Trust and sent to collaborators in Amsterdam University Medical Centre (AUMC) to evaluate the changes in the composition and the function of the respiratory microbiome after the initiation of Kaftrio. AUMC have developed a novel method to standardize the procedure of trapping volatile organic compounds (VOCs) in exhaled breath onto sorbent tubes. Kaftrio is shown to have a major effect on pulmonary function, mucociliary clearance and reduction in sweat chloride test. VOCs can give insight into both the metabolic pathways and inflammation caused by microorganisms in the lungs that are commonly associated with CF.

Airway Inflammation

Aliquots of sputum supernatant ± protease inhibitors from each individual and time point will be sent to the laboratory of [name] and [name], at Queens University Belfast for analysis of inflammatory markers. Although inflammation is a major feature of CF there is no universally accepted way to measure it in subjects. On the basis of our experience and data to date, we have compiled a compendium of airway inflammation biomarkers of particular relevance to the CF lung (Table 7). The sample collection and storage plan for RECOVER will allow further expansion of this panel based on initial findings or future work.

Host defence family	Members	Method of analysis
Proteases and neutrophil products	Serine (neutrophil elastase, proteinase 3), cysteine (cathepsin S, B, L), matrix metalloproteases (MMP-8, -9, -12), myeloperoxidase (MPO)	Fluorogenic activity assays, ELISA
Antiprotease	SLPI, cleaved-SLPI, tissue inhibitor of metalloproteases (TIMP-1, -2), cystatin SN and C	ELISA, Western blotting

P.I. [name]

		, ,
Cytokines/chemokines	Interleukins -1β, -6, -8	Luminex MILLIPLEX
		multianalyte panel assays

Table 7. Host factors to be analyzed in CF sputum supernatant and nasal lavage

All data will be compiled on an on-going basis over the course of the task and inputted into the study database as samples are analyzed. We would hope, that through this comprehensive approach, and analysis of the data comparing individuals before and after treatment that we will gain important insights that could be of benefit in terms of monitoring of disease activity and burden in individuals with CF.

Fraction of Exhaled Nitric Oxide (FeNO)

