FeNO will be measured with the Niox VERO[™] device via a mouthpiece in spontaneously breathing children in all centres by a trained research coordinator according to manufacturer's instructions. FeNO will be assessed at minus three months, baseline, 6 months and one year after commencement of Kaftrio. FeNO levels will be compared to markers of lung function, particularly LCI, markers of lung inflammation and total and specific (particularly air trapping) CT scores.

Airway Arginine/NO Metabolism

Sputum samples will be collected and processed as per TETRIS protocol and then shipped for central storage at NCRC. An aliquot of sputum supernatant from each individual and time point will be sent to the laboratory of Drs [name] and [name] in Toronto, Canada, for centralized testing of indices of L-arginine and NO metabolism.

Sputum concentrations of NO metabolites nitrate and nitrite will be measured by Griess reagent as previously reported(142). Concentrations of arginase 1 will be determined by use of a commercial ELISA kit (human ARG-1 ELISA KIT, cat.# ELH-ARG1-1, RayBiotech).

Liquid chromatography-mass spectrometry (LC-MS/MS) will be used to quantify L-arginine metabolites as previously reported(75). L-arginine, L-ornithine, L-citrulline and asymmetric dimethylarginine (ADMA) will be measured, as well as the L-ornithine downstream products proline and the polyamines putrescine, spermine and spermidine(143).

Changes in laboratory outcomes (NO metabolites, arginase and L-arginine metabolites) between visits will be assessed using paired t-tests and Wilcoxon sign-rank tests for skewed distributions, or ANOVA. Correlations between measure laboratory outcomes and clinical outcomes (FeNO and pulmonary function) will be assessed with the Pearson's correlation coefficient.

The ability of NOS to produce NO depends on the availability of substrate L-arginine as well as the competitive inhibitor ADMA. Therefore, the ratio of L-arginine over ADMA (L-arginine/ADMA) is used as a marker of NOS impairment(83, 144). The L-ornithine derived polyamines are important in tissue repair and can act as inhibitors of NOS and contribute to airways obstruction(143), while proline contributes to collagen deposition and airway remodeling. Therefore, these ratios will also be used for the analyses.

Risks in Airway Inflammation data collection

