The main foreseeable risk factor in this part of the study is the inability to collect a sputum specimen. Many patients, especially younger or healthier ones may not routinely produce sputum on a regular basis. We further suspect that, in light of the significant improvements in clinical outcomes demonstrated already for Kaftrio, that many individuals will go from being sputum producers to non-producers on treatment. We will work closely with the clinical teams to ensure that sputum specimens are optimized in terms of the split between laboratory and research processing. Each clinic has their own mechanism for trying to facilitate sputum production either at clinics or annual assessment – we will work with teams to ensure that saline induction, where used, can be facilitated by the research team to try to ensure a suitable sample sputum volume can be collected for all uses. We are aiming to collect 4 sputum samples over 2 years for RECOVER, with the baseline and year one samples prioritized. Where possible the research team will work with the subjects and clinical teams to ensure that all efforts are made to obtain a sufficient sample volume at these timepoints in particular, including sputum induction. The use of the TETRIS sputum processing protocol will mean that it is acceptable to use

P.I. [name] spontaneously produced and induced sputum interchangeably when obtaining samples. This will greatly facilitate optimal sampling.

We expect that an incomplete set of samples will be collected and have factored this into our study calculations in terms of numbers and budget. With a recruitment of 150 individuals to the advanced group we would ideally expect 600 sputum samples and 414 nasal lavage samples to process (1014 total). In reality we estimate that it is likely that we will have 90% of individuals produce one sputum sample, 80% to produce 2 samples, and 70% to produce 3 samples and 60% to produce 4 samples. We estimate that 80% of eligible individuals will produce one nasal lavage sample, 70% two samples and 60% three samples. The main foreseeable risk factor with nasal lavage is aspiration of isotonic saline. In practice this is a very similar procedure to sinus rinse which is commonly performed by many people with CF on a daily basis where we see almost no adverse effects in those who learn how to do the procedure. It is likely that some people may find this an uncomfortable or awkward procedure and elect not to do it.

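### Spontaneous and induced sputum are treated as interchangeable although the protocol expects ETI to shift participants from one to the other, so before/after sputum marker concentrations cannot separate collection method from drug effect

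*Protocol*

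**What the plan says.** All of this comes from the protocol, mostly Specific Aim 3.

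- **Collection (Sputum processing).** Sputum may be spontaneous or induced. The trigger for induction is non-production: "If a subject is not in a position to produce sputum, the research nurse/coordinator will arrange for sputum induction to be carried out". The method is stated as "Sputum induction will be performed by using 7% hypertonic sodium chloride solution will be nebulized for 15 minutes".
- **Expected effect of treatment (Risks in Airway Inflammation data collection).** The investigators suspect that "many individuals will go from being sputum producers to non-producers on treatment". Baseline and year one are the prioritised samples, and induction is named among the efforts to secure them.
- **Equivalence (same section).** One sentence, split by a page break, reads "The use of the TETRIS sputum processing protocol will mean that it is acceptable to use" and then "spontaneously produced and induced sputum interchangeably when obtaining samples". No comparative data are given.
- **Comparison (Airway Inflammation; Airway Arginine/NO Metabolism).** The inflammatory markers rely on "analysis of the data comparing individuals before and after treatment". Changes in NO metabolites, arginase and arginine metabolites "between visits will be assessed using paired t-tests and Wilcoxon sign-rank tests for skewed distributions, or ANOVA".
- **General model (Statistical Analysis).** Mixed models adjust for demographic and co-morbidity covariates. Collection method is not named.
- **Status (Primary and Secondary Outcomes).** "Sputum inflammatory markers" is listed as a secondary outcome.

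Neither Aim 3 nor the biosample collection plans state that the collection method must be recorded for each sample.

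**The concern.** A within-person before/after comparison attributes to treatment whatever changes between the visits. Here the protocol itself predicts that the way the sample is obtained will change between visits, and in one main direction: some participants who expectorate spontaneously at baseline will need induction on ETI.

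Several sputum outcomes are concentrations, and no dilution marker or normalisation is described. If induced sputum reads differently from spontaneous sputum, through added saline or because different secretions are sampled, the average concentration moves even when inflammation has not. A lower reading would resemble the anti-inflammatory effect that Aim 3 looks for.

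No concurrent untreated group is described for these markers, so nothing in the comparison would reveal the artefact. If the method was not recorded, no later analysis could examine it, and the banked aliquots would carry the same gap.

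**Working it through.** **The plan's own figures.** The ideal count of sputum samples reproduces: 150 advanced-group participants × 4 samples = 600. The stated yields of 90%, 80%, 70% and 60% give 150 × (0.9 + 0.8 + 0.7 + 0.6) = 450. No power or effect-size calculation for a sputum marker appears, so there is no planned effect to set a bias against.

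**Following the text**

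1. Non-production leads to induction (Sputum processing).
2. ETI is expected to raise non-production (Risks section).
3. So ETI is expected to raise the share of induced samples after treatment.
4. The contrast is before versus after, with no method term named.
5. Any systematic difference between methods therefore enters the treatment contrast.

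**Size, by assumption.** Let *f* be the net share of pairs that move from spontaneous to induced, and *r* the ratio of induced to spontaneous concentration. The documents give neither. With no drug effect, the geometric mean after/before ratio is *r*^*f*, and the apparent fall is 1 − *r*^*f*.

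| *r* (assumed) | *f* (assumed) | *r*^*f* | apparent fall |
|---|---|---|---|
| 1.0 | any | 1.000 | 0% |
| 0.8 | 0.3 | 0.935 | 6% |
| 0.8 | 0.6 | 0.875 | 13% |
| 0.5 | 0.3 | 0.812 | 19% |
| 0.5 | 0.6 | 0.660 | 34% |

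**Effect on a paired test.** A simulation of 20,000 trials per setting applied a two-sided 5% paired t-test to log concentration, with no drug effect. It used 90 pairs (60% of 150) and an assumed SD of paired log differences of 0.8 or 1.2.

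| *r* | *f* | false positives, SD 0.8 | false positives, SD 1.2 |
|---|---|---|---|
| 1.0 | 0.4 | 4.9% | 5.2% |
| 0.8 | 0.2 | 8.4% | 6.3% |
| 0.8 | 0.4 | 18.1% | 10.9% |
| 0.5 | 0.6 | 99.4% | 88.2% |

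These figures illustrate the mechanism and do not estimate the bias in this study.

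**How plausible is the upper end?** Table 6 gives 64 of the 150 advanced places to ages 6–11 and 86 to ages 12 and over. Participants induced at both visits do not contribute to *f*. If the children were all induced at both visits (an assumption), *f* could not exceed 86/150 = 0.57, and would reach that only if every older participant switched. The 34% is therefore an outer value.

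**The case against.** **TETRIS may equalise the two sample types.** The protocol's summary of TETRIS begins at collection and admits both routes. The section on arginine and NO metabolism says samples are both collected and processed under it, and the title of the cited reference mentions collection as well as processing. So it would be wrong to say that TETRIS covers only what happens afterwards. This stands: equivalence cannot be ruled out, and at *r* = 1 there is no bias. But the steps described (ice, homogenisation of plugs in buffered saline, centrifugation) do not show that a difference arising at collection is removed.

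**Direction and size are assumed.** This also stands. A reader might infer that a fall in sputum markers in this study would be an artefact, or that the bias must be downward. The documents support neither; they show only that the comparison cannot exclude it.

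**Not everything is exposed.** The L-arginine/ADMA ratio and other ratios are also planned, and simple dilution cancels in a ratio. A reader might extend the calculation to the sputum microbiome, but *r*^*f* describes concentration, not community composition. A reader might also conclude that Aim 3 as a whole could be wrongly answered. Aim 3 also draws on FeNO, nasal lavage by one fixed technique, and clinical cultures.

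**Adjusting for method is not a clean remedy.** This is the strongest point, and it stands. If ETI changes the method, method is a post-treatment variable. Those who stop producing sputum may be the best responders. Same-method pairs would then tend to leave them out, and a method term could absorb real effect. Replacing the planned paired tests with an adjusted model would trade one possible bias for another.

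**Analysis detail may sit in an SAP.** Further covariates and sensitivity analyses could be there, and the eCRF may already hold a method field. Neither is at hand. The protocol itself nevertheless declares the two sample types interchangeable and states no requirement to record which was obtained.

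**Conclusion.** The point holds in a limited form. By the protocol's own account, collection method is expected to shift from before to after ETI. The uncontrolled comparisons of sputum marker concentrations cannot separate that shift from a drug effect unless spontaneous and induced sputum give equal readings, and that equality is asserted without data.

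The size and direction of any bias are unknown from the documents. Under the assumed ranges (*f* 0.3–0.6, *r* 0.5–0.8) the apparent fall is 6% to 34%; at *r* = 1 it is zero. The point concerns the secondary sputum concentration outcomes. Ratio outcomes are less exposed, and FeNO, nasal lavage, LCI and CT are not affected.

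It does not follow that the planned paired analysis should be dropped or that a method-adjusted estimate would be the correct one. What the study needs is the means to show whether a change in sputum markers depends on how the sample was obtained.

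**What to change.** 1. In Sputum processing and in Risks in Airway Inflammation data collection, require spontaneous or induced to be recorded on the eCRF for every research sputum sample. Replace the unqualified statement of interchangeability accordingly.
2. Report the proportion of samples obtained by each method at each visit.
3. Keep the planned before/after analysis in Airway Arginine/NO Metabolism. For the sputum concentration outcomes, add a pre-specified sensitivity analysis giving the before/after contrast within same-method pairs. A model with a method term is optional.
4. State that method is itself affected by treatment, so these analyses may select against responders or absorb part of a true effect. They are to be read beside the main result, not in place of it.
5. State that a fall in sputum markers will be attributed to reduced inflammation only with the sensitivity result shown alongside.

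The cost is one data field and no added procedure. The sensitivity analysis will have fewer pairs and wider intervals, and it carries the selection caveat in item 4. If the method was not noted for samples already taken, it may be recoverable only in part, and the extent of that gap should be reported.

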In 2006 our collaborators ([name] and [name]) established the Irish Longitudinal Study on Cystic Fibrosis Liver Disease. The aim of this national cohort study was to determine the outcome and risk factors for liver disease in Cystic Fibrosis. All centres both adult and paediatric providing care for persons with CF (PWCF) are involved in the study. Between 2006-8 PWCF under 18 years of age attending any Irish Pediatric Centre were enrolled prospectively in a 20-year longitudinal study to examine the risk factors and outcome for CFLD. 522 (93% of eligible population) agreed to participate. Children so far have had nutritional, clinical, biochemical and radiological assessments in 2006/8; 2011/2 and 2016/17. In the intervening years data on height, weight, pulmonary function, laboratory parameters and mortality were obtained through our collaborators at the Cystic Fibrosis Registry of Ireland (CFRI) with the consent of our research participants.

In the first prospective study on CFLD we have confirmed, that despite significant investment in services for PWCF in Ireland the outcome for CFLD is poor for children who develop CFLD (Figure 3). Over a relatively short follow-up (median 10-year follow-up period the mortality rate for those classified as having CFLD in 2007 was 7.75 (95%CI 4.6-12.25) per 100 person years of follow-up compared to 2.3 (95% CI 1.4 – 3.6) in those with non-specific liver disease compared to 1.13 (95% CI 0.77- 1.59) per 100 person years of follow-up in those with no evidence of liver disease. The mortality rate difference between those with no evidence of liver disease.

P.I. [name]

disease and those with CFLD was 6.63 (95% CI 3.0-10.2; p,0.001). There was a similar mortality rate difference between those with nonspecific liver disease and CFLD was 5.4 (95%CI 1.7-9.1 p<0.01). This longitudinal dataset will provide an ideal backdrop with which to understand the impact of CFTR modulation on liver disease parameters in CF.

[figure not shown]

Figure 3. Survival in Irish PWCF between 2008-2018 with no liver disease (blue), non-specific liver disease (green) and CF liver disease (red).

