The aim of the CF liver disease arm of RECOVER is to gain a greater understanding of the changes in CF liver manifestations in people on CFTR modulator therapy. This is done by analyzing data from liver ultrasounds, liver function tests and other blood tests. For the parent study, LFTs are monitored every 3 months for the first year and at year two. Liver exams and ultrasounds will be carried out at baseline, year one and year two. For the extension study, LFTs are monitored annually as part of normal clinical care. Ultrasounds will be performed where indicated as part of normal clinical care at the participating center (most RECOVER sites perform annual ultrasound screening).

Liver Examination for the Parent Study

As part of the formal assessment of classification of CFLD (CFLD, non-specific [NSCFLD] and No LD), site investigators at all sites will be asked to clarify specifically on physical examination whether there is a hard liver and splenic enlargement at study baseline and at year one and two. Specific guidance will be provided around clinical examination via a training video by the lead hepatologist (BB) on the study. The baseline liver disease status of participants in the Republic of Ireland will be updated/confirmed using data from the Irish longitudinal study on cystic fibrosis liver disease study (ILSCFLD) based on previously collected data. The data from examination, ultrasound and blood tests will be collated on the CFLD worksheet (figure 7). A single paediatric (BB) and a single adult (AM) hepatologist will review the worksheets together in batches after each assessment window and determine which group subjects should be allocated to. If there is a discrepancy between ILSCFLD allocation and RECOVER baseline allocation these will be reviewed as a group by the study hepatologists and a confirmed allocation agreed to enable longitudinal assessment using ILSCFLD data.

CFLD V	Vorkshe	eet Now	el Modulato	r Therapy C	tcomes with ombinations rstic Fibrosis	REC	Øv	P.I. Pau
Study Code		Study visit			Age at asses	ssment		
Clinical exami	nation							
Was clinical e	xamination per	formed?	YES	NO				
Was there a h	ard liver edge?	?	YES	NO				
Was the splee	en abnormally l	arge	YES	NO				
Liver Ultrasou	ind							
Did the subje	ct have a Liver	USS?	YES	NO				
Abnormal ech	otexture		YES	NO				
Nodules			YES	NO				
Spleen size (c	m)				Integer with	one decimal		
Portal Flow			NOR	MAL	IMPAIRED	REVERSE		
Liver function	tests/other							

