At the end of the parent study, the liver disease status of participants (CFLD, non-specific [NSCFLD] and No LD) will be updated based on study assessments and review of study worksheets. Proportions of subjects in each group will be compared before and after modulator therapy in addition to determining how many individuals from each given group move to another group on ETI. This will be compared to historic natural history data from the ILSCFLD study for ROI participants.

Classification as part of extension study

Classification will be assigned to each participant as having CFLD, NSCFLD or NoLD annually during the extension study as above.

Specific Aim 6 for Parent Study and Extension Study – Pulmonary Exacerbations and Antibiotic Use

IV Antibiotic Therapy

The number of courses of IV antibiotics (hospitalizations and home IVs) and their indication (elective or unplanned) will be recorded over the duration of the study. This data will be collected in conjunction with clinical staff at local sites. The number (and number of days) of IV antibiotic courses over the length of the study timeframe will be compared with the number of IV antibiotic courses (and days) in the five years prior to commencement of ETI. Some individuals will have started on previous generations of CFTR modulators in the two to three years prior to the initiation of ETI, in which case data will be available for IV antibiotic courses before and on previous CFTR modulator therapy as well as on ETI.

Oral Antibiotic Use

The number of courses, total number of days and type of oral antibiotics will be collected from pharmacy records submitted with parent/guardian consent (and ethical approval) at the end of the study period as part of the adherence arm of RECOVER. The number of courses and number of days of oral antibiotic use will be documented in the eCRF. Given the complexity of the system at UK sites for collection of this information, data on oral antibiotic use from community pharmacies will be collected only from sites in Ireland.

Analysis of Data

Given the depth of information collected through RECOVER we will be in a position to compare antibiotic use to pulmonary outcome measures such as lung function, structure and inflammation, and non-pulmonary indices such as sweat chloride and medication adherence.

Definition of Exacerbation

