Participant data will be coded and only indirectly identifiable. Confidentiality of the participants is ensured by using a specific code that does not carry any personal identifier. The link between the codes that could identify the donor, enabling correlation with the data is only accessible to authorised personnel at the collection sites but not to the scientists involved in the RECOVER project or anyone in a receiving hospital, or institution. Data analysis will be performed in a blinded manner. Results of a study may be communicated at scientific meetings and will contribute to the scientific literature. At no time will this be done in such a way that an individual participant may be identified.

Internal Data Sharing:

For network organization, coordination of materials and documentation exchanges and data that is to be shared amongst the consortium (e.g. project results, deliverables, documents, datasets, reports, SOP's, presentations, publications, MTA's, contracts, communicating agendas, minutes of meetings, up-to-date information on the project etc), a secure GDPR and HIPPA compliant cloud platform with end to end encryption will be used (Tresorit) for efficient transfer between partners. Partners will be advised that documents containing data to be shared are saved in an appropriate format, encrypted, uploaded to Tresorit with appropriate nomenclature. This will provide for a data standardization concept to facilitate data queries, transfer and joint analyses. This data sharing platform is secured using restricted login details accessible only to consortium partners, controlled by the RECOVER Management Group. However, this platform will not be used for data storage long-term. Each individual partner is responsible for their own (meta)data collection, storage and security.

Sensitive Personal Genetic data

Participants will be asked to explicitly consent to the collection of their genetic material or data for the purposes of the study. They will be assured that their material/data will be pseudonymised to protect their privacy, and securely stored, with access tightly controlled, to safeguard the confidentiality of their genetic material and data with regard to both family members and others. The link between the codes that could identify the donor, enabling correlation with the data is only accessible to authorised personnel at the collection sites.

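### Liver class may rest on different evidence at baseline and at year 2 for Irish participants with earlier cohort data, and for everyone it is allocated by readers who can see the visit

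*Protocol*

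**What the plan says.** Under Liver Examination for the Parent Study (Specific Aim 5), examination, ultrasound and blood results go onto a one-page worksheet (Figure 7) headed with study code, study visit and age at assessment. One paediatric and one adult hepatologist "will review the worksheets together in batches after each assessment window and determine which group subjects should be allocated to". The classes are CFLD, non-specific disease (NSCFLD) and no liver disease (NoLD).

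The same section adds a source at baseline: "The baseline liver disease status of participants in the Republic of Ireland will be updated/confirmed using data from the Irish longitudinal study" on CF liver disease (ILSCFLD). "If there is a discrepancy between ILSCFLD allocation and RECOVER baseline allocation these will be reviewed as a group by the study hepatologists", and one confirmed class is agreed so that ILSCFLD data can be used for longitudinal assessment.

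Under End of parent study assessment, liver status "will be updated based on study assessments and review of study worksheets". ILSCFLD is not named as a source there. Then: "Proportions of subjects in each group will be compared before and after modulator therapy", together with counts of people who move between groups. For Republic of Ireland participants the result is also set against ILSCFLD natural history.

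The one sentence on blinding, under Confidentiality and Data Coding, is "Data analysis will be performed in a blinded manner". It does not mention class allocation.

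**The concern.** A before/after comparison without a concurrent control is interpretable only if both classes are produced in the same way. Two features put that in doubt.

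First, for some participants the baseline class can draw on years of earlier findings, while the year-2 text names study data only. NSCFLD is the exposed category because, according to the CF Liver Disease background section, it rests on non-specific ultrasound or biochemical signs. How often it is assigned depends on how many assessments are pooled. The protocol does not say whether the worksheet class or the ILSCFLD-confirmed class is the *before* value.

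Second, for all participants, reading in batches after each window with the visit on the sheet tells the readers whether a sheet is pre-treatment or on-treatment. Improved liver outcome is a stated hypothesis.

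At stake are the class proportions and transitions in Aim 5, which could show movement produced by the classification procedure.

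**Working it through.** **No design figure to reproduce.** The protocol gives no sample size or power for liver class. The ILSCFLD proportions it quotes do reproduce: 28/445 = 6.29%; 15/110 − 13/335 = 9.76 points; 119/335 = 35.5%.

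**Who is affected by the evidence difference.** The preliminary results section says: "Between 2006-8 PWCF under 18 years of age attending any Irish Pediatric Centre were enrolled prospectively in a 20-year longitudinal study". The protocol places European approval of ETI in 2020 and expects the 6-11 cohort about a year later. A child aged at most 11 in 2021 was born in 2009 or later, so was not enrolled as described. UK participants, Belfast included, are outside the step. It therefore reaches Republic of Ireland participants in the 12+ cohort who were under 18 in 2006-8. Their number is not given.

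**Evidence by visit**

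| | Baseline | Year 2 |
|---|---|---|
| RECOVER worksheet | yes | yes |
| ILSCFLD history | yes, Republic of Ireland | not named |
| Agreement step for discrepancies | yes | not named |
| Visit and age visible to readers | yes | yes |

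**Illustration with no true change and no drug effect.** Assumptions:
- Someone with NSCFLD shows it at a single assessment with probability s. The documents give no value, so s runs from 0.70 to 0.95.
- Assessments are independent and there are no false positives.
- At baseline any abnormality counts, over the three ILSCFLD rounds ("biochemical and radiological assessments in 2006/8; 2011/2 and 2016/17") plus the baseline worksheet. At year 2 only that visit's worksheet counts.
- True NSCFLD prevalence is 110/(335 + 110 + 35) = 110/480 = 22.9%, from the ILSCFLD class sizes.

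Baseline share = 22.9% × [1 − (1 − s)^4]. Year-2 share = 22.9% × s.

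| s | Baseline | Year 2 | Spurious fall (points) |
|---|---|---|---|
| 0.70 | 22.7% | 16.0% | 6.7 |
| 0.80 | 22.9% | 18.3% | 4.5 |
| 0.90 | 22.9% | 20.6% | 2.3 |
| 0.95 | 22.9% | 21.8% | 1.1 |

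Nearly all movement is downward. At s = 0.80, 4.6 per 100 move down (22.9 × 0.9984 × 0.2) and 0.03 per 100 move up (22.9 × 0.0016 × 0.8). If 100 participants had such history (an assumption), the expected McNemar statistic would be (4.58 − 0.03)/√(4.58 + 0.03) ≈ 2.1. It would be about 2.5 at s = 0.70 and 1.5 at s = 0.90.

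**Same rule at both visits.** With one worksheet against one worksheet, movement is 22.9 × s(1 − s) per 100 in each direction: 4.8, 3.7, 2.1 and 1.1 for the four values of s. The expected net change is zero.

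**Other ways to fill the gaps.** Suppose ILSCFLD says NoLD, the baseline worksheet says NSCFLD and NoLD is agreed. An identical year-2 worksheet then looks like worsening. If *updated* means the earlier class is carried forward, an NSCFLD label can persist despite normal findings and hide improvement.

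**The case against.** The strongest reply is that the asymmetry is inferred. Baseline is also classed from the worksheet, ILSCFLD only updates or confirms that class, and *updated* at year 2 may carry earlier evidence forward. The agreed class has a stated purpose, longitudinal assessment with ILSCFLD data, so the before/after table may already be meant to use worksheet classes. This stands to the extent that the protocol contains an unresolved ambiguity and not an explicit unequal rule. The choice of baseline class could be settled in an analysis plan. How the classes are generated and who knows the visit could not, because an analysis plan cannot mask a reading already done unmasked.

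A reader might go further in three ways that the documents do not support.
- *The procedure favours ETI.* Discrepancies are settled by agreement and can go either way, and the direction of any bias from knowing the visit is unknown.
- *The bias is 9 to 25 points.* With one earlier assessment counted at baseline only, p(1 − p) gives 0.09, 0.21 and 0.25 for p = 0.9, 0.7 and 0.5. Those are shares of people assumed to have stable, intermittently visible NSCFLD. At 22.9% prevalence they become about 2 to 6 points of those with ILSCFLD history. The 119/335 figure is movement from NoLD to non-specific signs over ten years and says nothing about reversion or repeatability.
- *The liver results as a whole are compromised.* The Liver Function Test and Ultrasound sections set out separate comparisons of AST/ALT, echotexture, portal flow and spleen size.

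Two further points stand. Worksheet items are mostly yes/no, banded or numeric and the two readers decide together, which limits discretion. The ILSCFLD comparison partly addresses spontaneous movement in Irish participants, but not a difference in rule between visits or knowledge of the visit.

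**Conclusion.** The point holds within limits. For Republic of Ireland participants with ILSCFLD data, the protocol names a source for the baseline class that it does not name for year 2, and it leaves open which baseline class is compared. For all participants the readers know the visit. Either feature can produce class changes without a drug effect.

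The size cannot be derived from the documents. The range of about 1 to 7 points of net NSCFLD share applies only to those with ILSCFLD history. It requires earlier abnormal findings to count at baseline only, and it rests on assumed sensitivities of 0.95 to 0.70, independent assessments and no false positives. Under the other readings the bias can run the opposite way. The effect of unmasked reading is not quantified. Class movement is one Aim 5 outcome among several.

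**What to change.** 1. For the before/after proportions and transitions, allocate baseline, year 1 and year 2 by one written rule from that visit's worksheet, and state that this is the class compared.
2. Treat biopsy evidence identically at every visit. It is a CFLD criterion in the background section but has no field on the worksheet shown, so a strict worksheet-only rule could misclass biopsy-proven disease.
3. Keep the ILSCFLD-confirmed baseline class for the natural-history comparison, which is the use the protocol gives for it.
4. Have the same two hepatologists allocate the worksheets with study visit and exact age masked (age band shown) and in random order, including baseline sheets already read.

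The cost is protocol wording and a re-read of at most 254 × 3 = 762 one-page sheets, with no new test or reader. The final allocation has to wait for the year-2 sheets. Site examination and ultrasound remain unmasked, so masking the re-read removes only the bias that arises when the hepatologists allocate.
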